We propose to include all 1000 patients in assessment of patient-reported outcomes. Linear mixed effects models will be used to evaluate changes in symptoms over time on these instruments. For purposes of estimating available statistical power, we consider a hypothetical analysis comparing changes in endocrine symptoms from baseline to 3 months between Caucasian and African-American patients. Total score on the FACT-ES (FACT-B plus ES subscale) will be calculated. Psychometric properties of FACT-ES were reported by Fallowfield et al. (29). In that report, mean scores of 61.61 at baseline (standard deviation 6.65) and 57.03 at 12 weeks (standard deviation 9.03) were reported among 32 women (a decline of 4.52 points). Table 3 shows statistical power and differences in change from baseline that will be detectable assuming a two-sided t-test with 5% Type I error, 85% power, baseline standard deviation of 6.65, intrapatient correlations of 0.4 or 0.6, and QOL completion rates of 90% and 75% across the two time points. There will be good power to detect reasonable differences between groups in changes from baseline.

Table 3. Detectable Differences for an Example Patient-Reported Outcomes Analysis (85% Power)

Intra-Patient Correlation	Standard Deviation of Change	Completion Rate	N Caucasian Patients	N African- American Patients	Detectable Difference
0.4	7.285	90%	540	180	1.88
0.6	5.948	90%	540	180	1.54
0.4	7.285	75%	450	150	2.06
0.6	5.948	75%	450	150	1.68

Rev. 11/13

Similar analyses will be done for the FACT-B subscale and for the Trial Outcome Index, consisting of the FACT-B subscale along with the FACT-G Physical Wellbeing and Functional Well-Being subscales.

In E1Z03, the quality of life companion study to MA27, patients who reported being bothered by side effects of treatment were more likely to discontinue treatment. The impact of patient-reported outcomes, both side effects in general and joint pain in particular, on treatment discontinuation will be examined along with the genotype information to assess the relative significance of both.

Patients will be given a choice regarding their preference for submitting QOL instruments in paper form or electronically. If 90% or more of patients choose the electronic system and if the completion rate among those patients is greater than 90%, then the web-based system would be considered for future trials.

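### Table 3 takes the baseline SD of 6.65 at both time points although the same paragraph gives 9.03 at 12 weeks; with 9.03 the detectable differences are 21–23% larger

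*Combined protocol and SAP*

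**What the plan says.** The power illustration in Section 9.3 (Statistical Considerations For Patient-Reported Outcomes) is introduced as follows: "we consider a hypothetical analysis comparing changes in endocrine symptoms from baseline to 3 months between Caucasian and African-American patients". Its variability data come from a published validation of the FACT-ES: "mean scores of 61.61 at baseline (standard deviation 6.65) and 57.03 at 12 weeks (standard deviation 9.03) were reported among 32 women".

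Table 3 is then computed for a t-test, two-sided at the 5% level. The remaining inputs are given as "85% power, baseline standard deviation of 6.65, intrapatient correlations of 0.4 or 0.6". Questionnaire completion is taken to be either 90% or 75%. The table prints an SD of change of 7.285 for a correlation of 0.4 and 5.948 for 0.6. The detectable differences are 1.88 and 1.54 points with 540 and 180 patients, and 2.06 and 1.68 points with 450 and 150.

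The section concludes: "There will be good power to detect reasonable differences between groups in changes from baseline".

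**The concern.** The SD of a change score depends on the SD at each time point and on the correlation between them. The plan names only the baseline SD. It does not say that the 3-month SD is assumed equal to it, and it does not explain why the 12-week SD cited just before is left out. That SD is the plan's only estimate of follow-up variability, and it applies to the time point that Table 3 analyses.

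If scores spread out under treatment as the cited figures suggest, Table 3 understates the SD of change, and its detectable differences are too small for 85% power. Table 3 is the only numerical support shown for the favourable power statement on between-group differences in change.

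**Working it through.** **Inputs (all from Section 9.3).** SD 6.65 at baseline and 9.03 at 12 weeks (n = 32); r = 0.4 or 0.6; two-sided t-test, alpha 0.05, power 85%; groups of 540 and 180 (90% completion) or 450 and 150 (75% completion).

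**Formulas.**

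- SD of change = √(s₁² + s₂² − 2·r·s₁·s₂)
- Detectable difference ≈ (1.960 + 1.036) × SD of change × √(1/n₁ + 1/n₂). The results below use the noncentral t, which differs from this only in the third decimal.
- √(1/540 + 1/180) = 0.0861; √(1/450 + 1/150) = 0.0943

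**Step 1: reproduce Table 3.** With s₁ = s₂ = 6.65 the first formula reduces to 6.65 × √(2(1 − r)).

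- r = 0.4: 6.65 × √1.2 = 7.285 (printed 7.285)
- r = 0.6: 6.65 × √0.8 = 5.948 (printed 5.948)

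The detectable differences are 1.881, 1.536, 2.061 and 1.683, against the printed 1.88, 1.54, 2.06 and 1.68. The arithmetic is right for its inputs, and the match shows that 6.65 was used at both time points.

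**Step 2: use both cited SDs.** 6.65² = 44.22 and 9.03² = 81.54.

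- r = 0.4: √(44.22 + 81.54 − 48.04) = 8.816, which is 1.210 times the printed value
- r = 0.6: √(44.22 + 81.54 − 72.06) = 7.328, which is 1.232 times the printed value

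| r | Group sizes | Printed difference | Difference with 9.03 | Power at the printed difference |
|---|---|---|---|---|
| 0.4 | 540 / 180 | 1.88 | 2.28 | 69.7% |
| 0.6 | 540 / 180 | 1.54 | 1.89 | 68.4% |
| 0.4 | 450 / 150 | 2.06 | 2.49 | 69.7% |
| 0.6 | 450 / 150 | 1.68 | 2.07 | 68.0% |

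**Step 3: correlation that would restore the printed SDs.** Solving the first formula for r with s₂ = 9.03:

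- SD of change 7.285 needs r = 0.605
- SD of change 5.948 needs r = 0.753

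The plan attaches 0.4 and 0.6 to these two values.

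**Step 4: uncertainty in 9.03.** Assuming normality, the chi-square 95% interval for an SD of 9.03 from 32 women is 7.24 to 12.01. With 6.65 and r held fixed, power at the printed differences is about 82% at 7.24. At 12.01 it is 50% (r = 0.4) or 46% (r = 0.6).

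**The case against.** The strongest reply is that this is a planning assumption, not a contradiction. The table shows the SD of change in its own column, and 9.03 comes from only 32 women. A Pitman–Morgan test of equal paired SDs on these figures gives p = 0.073 at r = 0.4 and p = 0.042 at r = 0.6, so equal SDs are not firmly excluded. That stands, but 6.65 comes from the same 32 women. Choosing it for both time points, against the plan's own source, needs to be stated and justified, and it is not.

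Second, the table already spans part of the corrected range. With 9.03 and r = 0.6 the SD of change is 7.328, close to the printed 7.285. Power at 1.88 and 2.06 is then about 84.5%. This is true and softens the point: the shortfall is row by row at a given r, and what is new is the r = 0.4 case (2.28 and 2.49). The printed r = 0.6 rows remain too optimistic.

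Third, the baseline SD is uncertain too, with a 95% interval of 5.33 to 8.84 by the same method. If both SDs sat at their lower limits (5.33 and 7.24), power at the printed differences would be about 86–87%. So the statement that power stays below 85% holds only with 6.65 fixed.

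Fourth, the example is hypothetical, the planned analysis is a linear mixed model, and 1.89 to 2.49 points is still below the cited mean decline of about 4.5 points. All true. However, that decline is a change within one group, not a difference in change between groups. The documents give no minimal important difference for FACT-ES, so they neither confirm nor refute that the larger differences are reasonable.

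**Conclusion.** The point holds and is minor. Table 3 rests on an unstated assumption of equal SDs that does not agree with the 12-week SD in its own paragraph. With 9.03 at follow-up, the detectable differences are 21% (r = 0.4) and 23% (r = 0.6) larger, and power at the printed differences is about 70% and 68% instead of 85%.

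This assumes that the 3-month SD is 9.03, that the plan's correlations still apply with unequal SDs, and that both racial groups share one SD of change. The documents report no observed correlation. The favourable power sentence is not shown to be false, but the printed figures do not support it as they stand. The 1000-patient target and the SNP power in Section 9.1 do not depend on this table.

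**What to change.** Recompute Table 3 with both SDs: SD of change 8.816 (r = 0.4) and 7.328 (r = 0.6); detectable differences 2.28, 1.89, 2.49 and 2.07. State in the text that 6.65 (baseline) and 9.03 (12 weeks) are the SDs used, and restate the power conclusion against these differences. If the sponsor wants to keep the equal-SD rows, they can stay beside the new ones as a sensitivity case, with the assumption written out.

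The cost is two SDs of change, four detectable differences and one or two sentences. The stated differences become 0.35 to 0.43 points larger. Sample size, endpoints and analyses do not change.

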9.4 Safety Monitoring

Interim analyses of toxicity are performed twice yearly for all ECOG studies. Reports of these analyses are sent to the ECOG Principal Investigator or Senior Investigator at the participating institutions. Expedited reporting of certain adverse events is required, as described in Section 5.

9.5 Gender and Ethnicity

Based on prespecified accrual targets the anticipated accrual in subgroups defined by gender and race is:

Ethnic Category	Gender		
	Females	Males	Total
Hispanic or Latino	100	0	100
Not Hispanic or Latino	900	0	900
Ethnic Category: Total of all subjects	1000	0	1000
Racial Category			
American Indian or Alaskan Native	5	0	5
Asian	200	0	200
Black or African American	200	0	200
Native Hawaiian or other Pacific Islander	5	0	5
White	590	0	590
Racial Category: Total of all subjects	1000	0	1000

The accrual targets in individual cells are not large enough for definitive treatment comparisons to be made within these subgroups. Therefore, overall accrual to the study will not be extended to meet individual subgroup accrual targets.

9.6 Accrual Rates

We expect to accrue 500 patients per year for 2 years. Accrual of African American and Asian cohorts may take longer, but targeted strategies will be used to encourage enrollment to these cohorts.

10. Correlative Studies

NOTE: An informed consent must be signed prior to the submission of any samples,

including future laboratory studies.

NOTE: ECOG requires that all biological samples submitted be entered and tracked

via the online ECOG Sample Tracking System. An STS Shipping Manifest Form must be generated and shipped with the sample submissions. See

Section 10.3.

NOTE: Institutions outside of the United States and Canada must confer with the

receiving laboratory and the ECOG Coordinating Center regarding logistics

for submission of fresh samples.

10.1 DNA Polymorphisms Associated with AIMSS and Discontinuation of Aromatase Inhibitors

Pharmacogenomic predictors may be able to identify women at risk for AIMSS since genetic variants have already been identified that are associated with AI pharmacokinetics, with the effects of estrogen deprivation on bone and other phenotypes.

The goal of the correlative study is to validate previously identified associations between ten specific single nucleotide polymorphisms (SNPs) and discontinuation of treatment with aromatase inhibitors (Als) due to the development of musculosketal symptoms (MSS) among women with breast cancer. If these associations are confirmed, a marker could be identified that may serve as an indicator of increased risk for treatment discontinuation and related poor therapeutic outcome.

10.1.1 Sample Submission Schedule

Instructions to order kits are outlined below in Section 10.1.2.1.

NOTE: Due to funding restrictions multiple kit requests are not permitted. Additionally patients must be registered to or being worked up for the trial before submitting your kit

requests.

Questions are to be directed to the ECOG Immunological Monitoring and Cellular Products laboratory (IMCPL) ECOG study coordinator at [contact].

10.1.1.1 Blood for DNA must be collected at baseline (blood is strongly encouraged to be collected at baseline [after registration, prior to treatment] but may be collected at any other time point if unable to collect at baseline)for the mandatory genotyping assays outlined in Sections 1.1.2 and 10.2.

[name] Laboratory at the Indiana University Division of Clinical Pharmacology will perform the analysis.

- 10.1.1.2 Blood (serum) for banking for future research studies should be submitted at the following time points:
 - Baseline

Rev 11/13

- At Three (3) Months OR Onset of AIMSS (if prior to three [3] months)
- At Twelve (12) Months **OR** Discontinuation of Anastrozole due to AIMSS

NOTE: Blood samples are to be submitted from patients who answer "YES" to "I agree to provide additional blood for research."

10.1.2 Sample Preparation Guidelines

- 1. At Baseline ONLY the following MUST be submitted:
- One (1) FULL 10 cc YELLOW top ACD tube
- 2. At EACH time point listed above in Section 10.1.1.2 please submit the following (OPTIONAL):
- One (1) FULL 10 cc RED top tube

Please completely fill all blood tubes as full as possible.

Each tube must be clearly labeled to include:

- ECOG protocol number E1Z11
- ECOG five digit patient sequence number
- Patient initials
- Originating institution/investigator name
- Date and time drawn
- Collection time point

10.1.2.1 Shipping Kits

Specimen shipping kits must be requested from the IMCPL. Please fax the request using the Shipping Kit Request Facsimile Form (Appendix VI) to [contact] or call the IMCPL at [contact]. Please allow ten days for shipment and provide the following information:

- Study Number
- Participating Site Number
- Contact Person and Telephone Number

The kits will be shipped via FedEx Express Saver. Please plan ahead, priority overnight shipment is not possible.

All blood samples should be shipped the day of collection using the shipping kit. Follow shipping instructions provided in the kit carefully.

The shipping kit consists of the following:

- Insulated shipping container and packing material
- FedEx Priority Overnight return label
- Shipping Instructions
- Shipping Kit Request Form

10.1.3 Shipping Procedures

Log the samples into the ECOG STS the day of shipment. If the STS is unavailable, an ECOG Generic Specimen Submission Form (#2981) must be submitted with the samples. Once STS is available, retroactively log the shipment into STS, using the actual collection and shipping dates.

If the STS is unavailable, notify the IMCPL ECOG study coordinator by [contact]) using the Specimen Shipment/Requisition Form (Appendix V). If you are unable to get through to the laboratory by fax, telephone the ECOG study coordinator at [contact] and provide the tracking number.

Blood collected into the appropriate tubes should be sealed, wrapped and placed in the specimen shipper kit and shipped on the same day they are drawn by Federal Express Priority overnight courier using the return label provided in the kit. The yellow and red top tubes should be refrigerated immediately. Cool packs are not required as the Styrofoam shipper should protect the tubes for overnight shipment. Shipments must be timed to arrive during normal working hours and should be shipped in one box.

The laboratory will be open Monday through Friday to receive samples. Do NOT ship on Fridays or Saturdays, or the day before a legal holiday. Ship by overnight courier Monday - Thursday only to:

Immunologic Monitoring and Cellular Products Laboratory University of Pittsburgh Cancer Institute UPCI-IMCPL

ECOG Study Coordinator Hillman Cancer Center [name]

[contact] [contact]

An STS Shipping Manifest Form must be generated and shipped with all sample submissions.

NOTE: Blood should **NOT** be collected on Fridays. Please contact the IMCPL for further instruction.

Federal Guidelines for the Shipment of Blood Products:

Sites should follow IATA regulations for Packaging UN3372 shipments. Please refer to FedEx guidelines.

10.2 Pharmacogenomic Study Methods

10.1.4

10.2.1 Specimen Acquisition

Blood will be collected at baseline using yellow top tubes. Specimens will be shipped to the ECOG IMCPL at the University of Pittsburgh where DNA will be isolated and stored for subsequent shipment to [name] Laboratory at the Indiana University School of Medicine for genotyping assays. DNA concentrations will be determined using the Picogreen DNA quantification assay (Life

Rev. 11/13

Rev. 11/13

Technologies, Inc). This assay is based on the SYBR green fluorescence and provides the most accurate total DNA quantification measurements. DNA quality will be assessed by 260:280 nanometers absorbance and a subset of samples will be run on an agarose gel to assure that high quality high molecular weight DNA is being isolated.

10.2.2 Assay

The [name] Laboratory will use the OpenArray[™] platform for the genotyping assays. The instrument to be used has been purchased from Applied Biosystems, Inc. The custom designed genotyping arrays are mini Taqman[™] assays plated on the OpenArrays[™] in 33 nanoliter reaction volumes. The thermocycling is done in an ABI 9600 thermocycler and the resulting allele specific fluorescence is read in the OpenArray[™] reader. All equipment and reagents are purchased from Applied Biosystems, Inc. (a division of Life Technologies, Inc).

10.2.3 Assay Performance

The [name] Laboratory's previous studies using the OpenArray™ format have yielded call rates of >95% with accuracy of >98%. For quality control purposes, approximately 10-15% of the samples are regenotyped. Concordance rates of >98% are expected, but are usually 100%. Any discrepancies are resolved by DNA sequencing. Every assay contains a no template control (water in place of the DNA sample). The assays are not performed in a CLIA laboratory, and thus no results will be returned to patients or health care providers.

10.2.4 Scoring

Genotyping data results will yield one of three possible classifications: Homozygous wild-type (2 wild-type alleles), heterozygous (1 wild-type and 1 variant allele), or homozygous variant (2 variant alleles). The classification is determined based on the fluorescent values obtained from the allelic discrimination plots of the Taqman™ assays. These are standard assays used widely in the field for genotyping. Minor allele frequencies are expected to range from 10% to 38% based on prior studies in similar populations. This range of frequencies is high enough that an association between the polymorphism and the phenotype of treatment discontinuation due to AIMSS has potential utility. The rate of treatment discontinuation due to AIMSS is expected to be 20 to 30%.

10.3 ECOG Sample Tracking System

It is **required** that all samples submitted on this trial be entered and tracked using the ECOG Sample Tracking System (STS). The software will allow the use of either 1) an ECOG user-name and password previously assigned (for those already using STS), or 2) a CTSU username and password.

When you are ready to log the collection and/or shipment of the samples required for this study, please access the Sample Tracking System software by clicking https://webapps.ecog.org/Tst

Additionally, please note that the STS software creates pop-up windows, so you will need to enable pop-ups within your web browser while using the software. A

user manual and interactive demo are available by clicking this link: http://www.ecog.org/general/stsinfo.html Please take a moment to familiarize yourself with the software prior to using the system.

An STS generated Shipping Manifest Form should be generated and shipped with all sample submissions.

Please direct your questions or comments pertaining to the STS to [contact]

10.3.1 Study Specific Notes

An ECOG Generic Specimen Submission Form (#2891) will be required only if STS is unavailable at the time of sample submission. Indicate the appropriate Lab ID # on the submission form:

- 0009= ECOG Immunologic Monitoring and Cellular Products Laboratory
 - The day of shipment, notify the IMCPL ECOG study coordinator by [contact]) using the Specimen Shipment/Requisition Form (Appendix V). If you are unable to get through to the laboratory by fax, telephone the ECOG study coordinator at [contact] and provide the FedEx tracking number.

Retroactively enter all collection and shipping information when STS is available.

10.4 Banking

Blood samples collected will be retained at the ECOG IMCPL for use in future ECOG approved studies. If future use is denied or withdrawn by the patient, the samples will be removed from consideration for use in any future study.

10.5 Lab Data Transfer Guidelines

The data collected or generated on the above mentioned correlative studies will be submitted electronically via secure data portal to the ECOG Coordinating Center by the central laboratory on a quarterly basis.

Appendix I

Rev. 4/14 Informed Consent Template for Cancer Treatment Trials (English Language)
[Deleted in Addendum #3]

INFORMED CONSENT INTENTIONALLY REMOVED FROM PROTOCOL DOCUMENT

Appendix I was removed from the protocol document in Addendum #3 and is posted as a separate document on the ECOG website. This was removed from the protocol to comply with NCI formatting guidelines.

A Cohort Study to Evaluate Genetic Predictors for Aromatase Inhibitor Musculoskeletal Symptoms (AIMSS)

Appendix II

Patient Thank You Letter

We ask that the physician use the template contained in this appendix to prepare a letter thanking the patient for enrolling in this trial. The template is intended as a guide and can be downloaded from the ECOG web site at http://www.ecog.org. As this is a personal letter, physicians may elect to further tailor the text to their situation.

This small gesture is a part of a broader program being undertaken by ECOG and the NCI to increase awareness of the importance of clinical trials and improve accrual and follow-through. We appreciate your help in this effort.

[PATIENT NAME]	[DATE]
[PATIENT ADDRESS]	
Dear [PATIENT SALUTATION],	

Thank you for agreeing to take part in this important research study. Many questions remain unanswered in cancer. With the help of people like you who participate in clinical trials, we will achieve our goal of effectively treating and ultimately curing cancer.

We believe you will receive high quality, complete care. I and my research staff will maintain very close contact with you. This will allow me to provide you with the best care while learning as much as possible to help you and other patients.

On behalf of **[INSTITUTION]** and the Eastern Cooperative Oncology Group, we thank you again and look forward to helping you.

Sincerely,
[PHYSICIAN NAME]

A Cohort Study to Evaluate Genetic Predictors for Aromatase Inhibitor Musculoskeletal Symptoms (AIMSS)

Appendix III

Patient Pill Calendar

Pill Calendar Directions

- 1. Take your scheduled dose of each pill.
- 2. If you forget, the missed pills will not be taken later.

NOTE: Local study teams may use a different calendar format as long as drug dates/doses are recorded for study reporting/data completion.

Patient Pill Calendar

This is a calendar on which you should record taking the study tablet, anastrozole. You should take your anastrozole as directed by your doctor. Write in the date and your initials for each day during the month you took anastrozole. If you develop any side effects, please record them and anything you would like to tell the doctor in the space provided.

	Date		Patient Initials	Number of pills taken	Did you take brand or generic	Side effects (including unusual symptoms), other medications you have taken, or other notes	
DAY	Month	Day	Year			anastrozole	for your doctor.
1							
2							
3							
4							
5							
6							
7							
8							
9							
10							
11							
12							
13							
14							
15							
16							
17							
18							
19							
20							
21							
22							
23							
24							
25					_		
26					_		
27					_		
28					_		
29					_		
30							
31							

A Cohort Study to Evaluate Genetic Predictors for Aromatase Inhibitor Musculoskeletal Symptoms (AIMSS)

